1. PURPOSE OF THE STUDY

a. Brief Summary

To evaluate the antidepressant effects of daily active iTBS in adolescents and young adults with moderate to severe depressive symptoms.

b. Objectives

The investigators hope to learn if iTBS is an effective treatment for depressive symptoms in adolescents. This is important knowledge as many adolescents are intolerant to medications or do not want to receive medications for the treatment of depression.

c. Rationale for Research in Humans

Human subjects must be used since the efficacy of the iTBS procedure is being tested in adolescent humans.

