2. STUDY PROCEDURES

a. Procedures

Screening

Subjects will undergo medical, psychological and neuropsychological assessments to assure compliance with all inclusion and exclusion criteria. Eligible subjects will receive active iTBS.

TMS Treatment

All treatments and motor threshold determinations will be completed by physicians or other health care providers who have been trained to the process based on the MagVenture User Manual and certified by the department. All processes are consistent with the clinical use of the MagVenture MagPro rTMS research system.

iTBS sessions will occur approximately 2 days after the baseline session with week daily sessions delivered to left DLPFC over 6 weeks. We will start with the currently FDA approved iTBS protocol for adults. Stimulation will be administered using the MagVenture MagPro rTMS Research System at currently FDA approved parameters: 80% of the active motor threshold, 20 cycles of 10 bursts of 3 pulses at 50Hz delivered in 2 second trains with an 8 second inter-train interval. The stimulation will be applied for

3 min delivering a total of 1800 pulses/session. These stimulation sessions will occur daily (week days) for 6 weeks. Resulting in a total of 30 sessions. Motor Threshold (MT) Determination: MT Location and MT Level - The motor threshold location will be determined by visual confirmation of the location on the motor cortex that controls the abductor pollicis brevis (APB) muscle of the thumb. The resting MT level is the minimum power to produce a stimulation response 50% of the time.

Prophylactic use of acetaminophen or ibuprofen will be allowed for subjects reporting sensations at or near the stimulation site which are uncomfortable or painful. During the first week of treatment only, in the event that the subject cannot tolerate the treatment at these dose parameters, dose intensity may be titrated downward to 110% of the motor threshold, with all other dose parameters remaining the same.

Heart Rate Variability (HRV)

Participants will have their HRV measured before they receive any stimulation, at the end of each stimulation week and at the end of the six week treatment course. HRV will be measured using ECG electrodes attached to the wrists and an r-wave trigger device (neuroConn, Ilmenau, Germany). HRV will be measured when viewing videos depicting negative emotions (e.g. anger, fear) and when viewing neutral stimuli.

Structural/Functional Brain MRI

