Structural MRI comparisons will be acquired for subjects at the Cognitive Neuroscience Institute (CNI) on the Stanford campus. A consistent MRI technician at each study site will be requested for each of the study scans. Each subject will have a baseline scan and a post- treatment scan.

First-level models: We will use a canonical hemodynamic response function (HRF) convolved event-related model with temporal and dispersion derivatives to model the blood oxygen level dependent (BOLD) in the context of a generalized linear model. Temporal and dispersion derivatives will be treated as regressors of no interest. A region of interest (ROI) analysis will be performed using our established methods, to identify BOLD- dependent signal change in the dorsolateral prefrontal cortex, subgenual cingulate, and default mode network nodes (right, left). Beta values for each ROI will be extracted for each subject for regression analyses.

Details regarding neuroimaging:

The subjects will undergo an MRI scan of the brain that will require about 1 hour in the MRI scanner. A structural MRI scan, fMRI scan will be done using a 3T system at Stanford facilities.

During the scan, subjects will lie on the table in the magnet for approximately 30 minutes while the images are acquired. Subjects will wear earplugs to reduce the noise of the scanner. The standard of care regarding incidental findings that will be communicated to

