patient is as follows: The investigators for this project are not trained to perform radiological diagnosis, and the scans performed in this study are not optimized to find abnormalities. The investigators and Stanford are not responsible for failure to find existing abnormalities in your MRI scans. However, on occasion the investigator may notice a finding on a MRI scan that seems abnormal. When this occurs, a radiologist will be consulted as to whether the finding merits further investigation, in which case the principal investigator of the research study being conducted will contact the participant's primary care physician and inform them of the finding. The decision as to whether to proceed with further examination or treatment lies solely with the participant and his/her physician. The investigators, the consulting radiologist, and Stanford are not responsible for any examination or treatment that you undertake based upon these findings. Because the images collected in this study do not comprise a proper clinical MRI series, these images will not be made available for diagnostic purposes. In the event that a potential abnormality on the MRI images is detected by the researchers, the magnet manager, is to be notified immediately to report the potential issue. Films of images are not be provided to the researcher or volunteer scan subject as the images were obtained using a research MRI scan protocol and not from a clinically- ordered MRI scan protocol prescribed by a radiologist at Stanford.

b. Procedures to Minimize Risks

Outcome Assessments

Trained physicians and raters will administer all diagnostic assessments and clinical interviews determining study eligibility during screening. All study staff will be trained on study procedures.

Outcome screening will occur after both the Informed Assent/Consent Document and the HIPAA Authorization are signed. Baseline assessments will occur prior to the first iTBS treatment session.

The following outcome assessments will be completed: HAMD/MADRS structured interview, CDRS-R, CGI-S, and QIDS-A17-SR.

Safety Assessments

A physical and complete medical and psychiatric history will be obtained at the screening visit. Subjects will be evaluated clinically for adverse events at each visit. SAEs will be recorded as they occur and reported to the IRB within one business day of notification.

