The YMRS will be completed if the interval assessment of spontaneous adverse events indicates the potential occurrence of symptoms of mania or hypomania.

c. Use of Deception in the Study

No deception will be used.

d. Use of Audio and Video Recordings

No audio or video recording to be used.

e. Alternative Procedures or Courses of Treatment

Other treatments are available for the treatment of depression, including Psychotherapy or medications (tricyclic, SSRI, SNRI, antidepressants).

f. Will it be possible to continue the more (most) appropriate therapy for the participant(s) after the conclusion of the study?

When youth become adults, they can receive iTBS through TMS outpatient clinics throughout the peninsula.

g. Study Endpoint

The end of the study is defined as “the last visit of the last patient undergoing the study.” The end of study definition is for the entire study. The study is expected to start in spring 2019 and to be completed by the end of 2020. The study may be terminated if the study procedures are not being performed according to GCP, or if recruitment is slow.

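### The objective asks whether iTBS is effective, but the design has one active arm with no comparator or benchmark, and no primary depression scale or timepoint is named

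*Combined protocol and SAP*

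**What the plan says.** **Objective.** Section 1.b reads: "The investigators hope to learn if iTBS is an effective treatment for depressive symptoms in adolescents". Section 1.c gives the reason for using human subjects as "Human subjects must be used since the efficacy of the iTBS procedure is being tested in adolescent humans". Section 8.c again describes the treatment as under investigation for efficacy as well as safety, and the summary in 1.a sets out to evaluate antidepressant effects.

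**Design.** Under Screening in section 2.a: "Eligible subjects will receive active iTBS". No sham, randomisation, blinding, historical control, target response rate or success criterion is described for this study. Section 8.a plans 30 participants. The word pilot is applied to the study only in section 9.e.ii, on safety monitoring.

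**Outcomes.** Section 2.b says: "The following outcome assessments will be completed: HAMD/MADRS structured interview, CDRS-R, CGI-S, and QIDS-A17-SR". That makes four items, or five if HAMD and MADRS are counted separately. None is ranked.

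**Timing.** For the rating scales, section 2.b fixes the start: "Baseline assessments will occur prior to the first iTBS treatment session". HRV is timed "at the end of each stimulation week and at the end of the six week treatment course", and for imaging "Each subject will have a baseline scan and a post- treatment scan". Section 9.c provides for weekly symptom queries as part of risk management. Section 9.d asks participants who stop early to complete the final assessments within 2 days of their last session. Section 2.g is titled Study Endpoint but concerns only when the study closes: "The end of study definition is for the entire study".

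**The concern.** There are two defects. They are independent, because curing one would leave the other in place.

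1. **The objective goes beyond the design.** Whether a treatment is effective is a question about what would have happened without it. With one active arm and no benchmark, the study observes only total change. That total includes any placebo response, which section 3.a itself calls well known in open-label adolescent trials. It also includes the natural course of depression, and regression to the mean because entry requires CDRS-R above 40. As the objective is worded, improvement that would have happened anyway could be reported as effectiveness in adolescents.

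2. **No primary outcome is named.** With several unranked scales and no designated timepoint, the scale that looks best can be presented as the study's result, and nothing in the plan would show that it had been selected.

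**Working it through.** **Is there a figure to reproduce?** No. The 30 in section 8.a comes with no effect size, SD, response rate, alpha, power or dropout allowance. The only analysis text, in section 2.a, concerns fMRI; no analysis of the depression scales is described. The calculations below are illustrations of what the design can and cannot show.

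**Inputs**
- n = 30 (section 8.a), taking all 30 to have a final rating.
- Two-sided alpha 0.05 and a one-sample t-test on change from baseline (assumed).
- True iTBS effect 0; non-specific improvement d = 0.3, 0.5 or 0.8 SD of within-participant change (assumed range).

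**Step 1: how often would a pre-post test be significant if iTBS did nothing?** The test statistic follows a noncentral t distribution with 29 df and noncentrality d × √n, where √30 = 5.477. The critical value is t(0.975, 29) = 2.045.

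| d (assumed) | noncentrality | P(significant improvement) |
|---|---|---|
| 0.3 | 0.3 × 5.477 = 1.64 | 0.355, about 36% |
| 0.5 | 0.5 × 5.477 = 2.74 | 0.754, about 75% |
| 0.8 | 0.8 × 5.477 = 4.38 | 0.988, about 99% |

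With no change of any kind, the figure would be 2.5% in the direction of benefit. The excess is not a fault of the test, which correctly detects that scores fell. It cannot say why they fell.

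**Step 2: what can 30 participants deliver?** A mean change with a 95% CI of half-width t(0.975, 29)/√n = 2.045/5.477 = 0.373, or about 0.37 SD of change. That is a usable estimate of pre-post change.

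**Step 3: is a primary outcome fixed elsewhere in the document?**
- Section 2.b lists the scales with no order of importance.
- Section 2.g defines the end of the study, not an efficacy endpoint.
- Section 8.h.i uses CDRS-R as an entry criterion, and section 9.c uses HAMD and CGI-S to monitor for worsening. Neither use makes a scale primary.
- The term primary outcome appears only in section 3.a, for a cited adult trial.
- Section 9.d implies a set of final assessments but does not designate it as the primary timepoint.

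No section names a primary scale or a primary timepoint.

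**The case against.** **A single-arm pilot is a legitimate design.** This stands. No control arm is asked for. The fault is that sections 1.b, 1.c and 8.c promise an answer on efficacy, while pilot status appears only in the safety-monitoring text.

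**The objective is phrased as a hope, and no decision rule is stated.** This stands in part: the remedy is mainly one of wording. But that sentence opens the Objectives section, the claim recurs in 1.c and 8.c, and it governs how the result will be read.

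**CDRS-R is implicitly primary because it sets entry.** This does not stand. The document never says so, and other listed scales also have a role in monitoring.

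Stronger readings that the documents do not support:
- A reader might infer that no depression rating is taken at the end of the course. Section 9.d speaks of the final assessments as an existing set, and baseline ratings with a post-treatment scan point to a pre-post structure. The supportable statement is that no primary timepoint is designated.
- A reader might take the adult sham-controlled trial in section 3.a, where significance differed by scale, as evidence that scale choice would decide this study's result. Those are between-arm contrasts in 197 adults and do not show how within-arm change would behave in 30 young people.
- A reader might want a false-positive rate for choosing the best scale. That requires no change on any scale, which contradicts the expectation of non-specific improvement, and the plan states no test on the depression scales.
- A reader might borrow remission rates from section 3.a to size the problem. The adult sham-controlled figures and the small adolescent open-label figure (5 of 7) lead to very different pictures, the plan adopts neither as a benchmark, and neither is needed to show that a comparator is absent.

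**Conclusion.** Both defects hold. The stated objective cannot be answered by this design, and no primary scale or timepoint is fixed. They should be corrected before outcome data are examined, because a primary outcome named afterwards carries little weight.

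The 36%, 75% and 99% depend on the assumed size of non-specific improvement, the assumed test and a final rating on all 30 participants; they are not predictions. The direct conclusion, that change from baseline cannot be attributed to iTBS, needs none of these assumptions. The selection risk from unranked scales is real but is not quantified here. That the study is open-label is inferred from all participants receiving active treatment with no blinding described.

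**What to change.** **1. Objective.** Replace the text of 1.b along these lines: to estimate, in a single-arm open-label pilot, the mean within-participant change in depressive symptoms, with a 95% CI, over the 6-week iTBS course, and to describe tolerability; the design cannot attribute the change to iTBS. Align 1.a, 1.c and 8.c with it. Section 10 is a statement of possible benefit and may be aligned for consistency.

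**2. Primary outcome.** Before outcome data are examined, add a short paragraph that:
- names one of the listed scales as primary (if it is from the HAMD/MADRS item, says which);
- fixes the contrast as pre-treatment baseline to the final assessment at the end of the 6-week course;
- includes early discontinuers' final assessments (section 9.d) in the main estimate, with completers shown beside it;
- reports all other scales as supportive, whatever they show.

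The choice of scale is for the investigators. If it is CDRS-R, note that as the entry scale it is the most exposed to regression to the mean.

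**Cost.** A reworded objective and one paragraph; no extra patients or arm. The downside is a less favourable permitted conclusion: a pre-post change with its interval, not a finding that iTBS works.

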2. STUDY PROCEDURES

a. Procedures

Screening

Subjects will undergo medical, psychological and neuropsychological assessments to assure compliance with all inclusion and exclusion criteria. Eligible subjects will receive active iTBS.

TMS Treatment

All treatments and motor threshold determinations will be completed by physicians or other health care providers who have been trained to the process based on the MagVenture User Manual and certified by the department. All processes are consistent with the clinical use of the MagVenture MagPro rTMS research system.

iTBS sessions will occur approximately 2 days after the baseline session with week daily sessions delivered to left DLPFC over 6 weeks. We will start with the currently FDA approved iTBS protocol for adults. Stimulation will be administered using the MagVenture MagPro rTMS Research System at currently FDA approved parameters: 80% of the active motor threshold, 20 cycles of 10 bursts of 3 pulses at 50Hz delivered in 2 second trains with an 8 second inter-train interval. The stimulation will be applied for

3 min delivering a total of 1800 pulses/session. These stimulation sessions will occur daily (week days) for 6 weeks. Resulting in a total of 30 sessions. Motor Threshold (MT) Determination: MT Location and MT Level - The motor threshold location will be determined by visual confirmation of the location on the motor cortex that controls the abductor pollicis brevis (APB) muscle of the thumb. The resting MT level is the minimum power to produce a stimulation response 50% of the time.

Prophylactic use of acetaminophen or ibuprofen will be allowed for subjects reporting sensations at or near the stimulation site which are uncomfortable or painful. During the first week of treatment only, in the event that the subject cannot tolerate the treatment at these dose parameters, dose intensity may be titrated downward to 110% of the motor threshold, with all other dose parameters remaining the same.

Heart Rate Variability (HRV)

Participants will have their HRV measured before they receive any stimulation, at the end of each stimulation week and at the end of the six week treatment course. HRV will be measured using ECG electrodes attached to the wrists and an r-wave trigger device (neuroConn, Ilmenau, Germany). HRV will be measured when viewing videos depicting negative emotions (e.g. anger, fear) and when viewing neutral stimuli.

Structural/Functional Brain MRI

Structural MRI comparisons will be acquired for subjects at the Cognitive Neuroscience Institute (CNI) on the Stanford campus. A consistent MRI technician at each study site will be requested for each of the study scans. Each subject will have a baseline scan and a post- treatment scan.

First-level models: We will use a canonical hemodynamic response function (HRF) convolved event-related model with temporal and dispersion derivatives to model the blood oxygen level dependent (BOLD) in the context of a generalized linear model. Temporal and dispersion derivatives will be treated as regressors of no interest. A region of interest (ROI) analysis will be performed using our established methods, to identify BOLD- dependent signal change in the dorsolateral prefrontal cortex, subgenual cingulate, and default mode network nodes (right, left). Beta values for each ROI will be extracted for each subject for regression analyses.

Details regarding neuroimaging:

The subjects will undergo an MRI scan of the brain that will require about 1 hour in the MRI scanner. A structural MRI scan, fMRI scan will be done using a 3T system at Stanford facilities.

During the scan, subjects will lie on the table in the magnet for approximately 30 minutes while the images are acquired. Subjects will wear earplugs to reduce the noise of the scanner. The standard of care regarding incidental findings that will be communicated to

patient is as follows: The investigators for this project are not trained to perform radiological diagnosis, and the scans performed in this study are not optimized to find abnormalities. The investigators and Stanford are not responsible for failure to find existing abnormalities in your MRI scans. However, on occasion the investigator may notice a finding on a MRI scan that seems abnormal. When this occurs, a radiologist will be consulted as to whether the finding merits further investigation, in which case the principal investigator of the research study being conducted will contact the participant's primary care physician and inform them of the finding. The decision as to whether to proceed with further examination or treatment lies solely with the participant and his/her physician. The investigators, the consulting radiologist, and Stanford are not responsible for any examination or treatment that you undertake based upon these findings. Because the images collected in this study do not comprise a proper clinical MRI series, these images will not be made available for diagnostic purposes. In the event that a potential abnormality on the MRI images is detected by the researchers, the magnet manager, is to be notified immediately to report the potential issue. Films of images are not be provided to the researcher or volunteer scan subject as the images were obtained using a research MRI scan protocol and not from a clinically- ordered MRI scan protocol prescribed by a radiologist at Stanford.

b. Procedures to Minimize Risks

Outcome Assessments

Trained physicians and raters will administer all diagnostic assessments and clinical interviews determining study eligibility during screening. All study staff will be trained on study procedures.

Outcome screening will occur after both the Informed Assent/Consent Document and the HIPAA Authorization are signed. Baseline assessments will occur prior to the first iTBS treatment session.

The following outcome assessments will be completed: HAMD/MADRS structured interview, CDRS-R, CGI-S, and QIDS-A17-SR.

Safety Assessments

A physical and complete medical and psychiatric history will be obtained at the screening visit. Subjects will be evaluated clinically for adverse events at each visit. SAEs will be recorded as they occur and reported to the IRB within one business day of notification.

The YMRS will be completed if the interval assessment of spontaneous adverse events indicates the potential occurrence of symptoms of mania or hypomania.

c. Use of Deception in the Study

No deception will be used.

d. Use of Audio and Video Recordings

No audio or video recording to be used.

e. Alternative Procedures or Courses of Treatment

Other treatments are available for the treatment of depression, including Psychotherapy or medications (tricyclic, SSRI, SNRI, antidepressants).

f. Will it be possible to continue the more (most) appropriate therapy for the participant(s) after the conclusion of the study?

When youth become adults, they can receive iTBS through TMS outpatient clinics throughout the peninsula.

g. Study Endpoint

The end of the study is defined as “the last visit of the last patient undergoing the study.” The end of study definition is for the entire study. The study is expected to start in spring 2019 and to be completed by the end of 2020. The study may be terminated if the study procedures are not being performed according to GCP, or if recruitment is slow.

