Efficacy of TMS for the treatment of adolescent depression, for all TMS devices including the NeuroStar TMS Therapy® System, has been reported in two pilot clinical studies and in multiple case reports (Walter 2001; Bloch 2008; Wall 2011). These open-

label studies describe the treatment of 24 patients, ages 10-18. The 2011 Wall et al. open-label trial is the only study that used the NeuroStar TMS Therapy System. This study reported on the treatment of 7 antidepressant-resistant adolescents and demonstrated a robust response rate noted by 5 of 7 subjects achieving remission of depression, as rated using the Childhood Depression Rating Scale – Revised (CDRS-R). Furthermore, CDRS-R mean depression severity scores were significant by treatment 20 as compared to baseline with similar efficacy demonstrated using the patient reported Quick Inventory of Depressive Symptoms – Adolescent Version (QIDS-A17- SR). Placebo effects in open-label trials of adolescents are a well-known phenomenon. However, adolescents demonstrate enduring mood improvement for at least 6 months following their final acute treatment (session 30). Furthermore, 7 of 8 subjects completed the entire treatment course, with 1 patient exiting the study after only 5 minutes of treatment due to scalp discomfort and a perceived lack of improvement.

iTBS has been shown to be more effective at inducing antidepressant responses in adults than traditional rTMS. 3 minutes of iTBS induce equivalent antidepressant responses as 37 minutes of traditional rTMS stimulation (Blumberger et al., 2015) and lower stimulation intensities are required to induce antidepressant responses (Wu, Shahana, Huddleston, Lewis, & Gilbert, 2012).

The shorter stimulation times and the lower stimulation intensities required for iTBS in comparison to traditional rTMS make iTBS potentially advantageous method for adolescents with MDD. Traditional rTMS has been shown to be effective at reducing depressive symptoms in adolescents (Carpenter et al., 2012) but iTBS has not been trialled in adolescents with MDD. Initial trials investigating the safety of iTBS in adolescents have identified iTBS as minimal risk (Hong et al., 2015; Wu et al., 2012).

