4. RADIOISOTOPES OR RADIATION MACHINES

N/A

5. DEVICES USED IN THE STUDY**a. Investigational Devices (Including Commercial Devices Used Off-Label)**

Investigational Device 1	
Name:	TMS Magnet (MagVenture)
Description:	Transcranial Magnetic Stimulation
Significant Risk? (Y/N)	No
Rationale for Non-Significant Risk	Device within FDA specified parameters (iTBS).

b. IDE-Exempt Devices

N/A

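### The stated train pattern gives 600 pulses per session in about 3 min 20 s, but the protocol states 1800 pulses in 3 min: a threefold contradiction in the dose under test

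*Combined protocol and SAP*

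**What the plan says.** The dose is specified in one paragraph of section 2.a, under TMS Treatment. The train pattern is "20 cycles of 10 bursts of 3 pulses at 50Hz delivered in 2 second trains with an 8 second inter-train interval". The sentence after it gives the session as "3 min delivering a total of 1800 pulses/session". On frequency, the paragraph says "These stimulation sessions will occur daily (week days) for 6 weeks" and "Resulting in a total of 30 sessions", which is one session per weekday.

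Three other places depend on this paragraph without giving a cycle or pulse count of their own:

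- Section 3.a (Background) presents short sessions as an advantage of iTBS, reporting that "3 minutes of iTBS induce equivalent antidepressant responses as 37 minutes of traditional rTMS stimulation".
- Section 5.a classes the device as non-significant risk because it is used inside the FDA's parameters for iTBS.
- Section 9.a, under Seizures, refers back to the stimulation parameters already given, says no seizure risk is known for them, and says they match other iTBS protocols that received a minimal-risk designation.

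**The concern.** Two adjacent sentences define the same session and give different doses. The number of trains, the pulse total and the session length cannot all be true.

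This matters more than an ordinary slip because the regimen is the only thing the trial tests. All eligible participants receive active iTBS and no comparator is described. Someone who programs 20 trains and someone who programs enough trains to reach 1800 pulses would each be following a clause of the protocol, at doses a factor of three apart. The protocol does not ask for the delivered pulse count to be recorded, so it does not ensure that the dose actually given could be recovered at analysis.

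The risk arguments in sections 5.a and 9.a also lean on these parameters. An IRB cannot check a claim that the parameters are within specification when the paragraph supports two values. The participants include minors aged 12 to 17.

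**Working it through.** **Inputs**, all from section 2.a, TMS Treatment:

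| Quantity | Value |
|---|---|
| Cycles (trains) per session | 20 |
| Bursts per train | 10 |
| Pulses per burst | 3 |
| Train length / inter-train interval | 2 s / 8 s |
| Stated session length | 3 min (180 s) |
| Stated pulses per session | 1800 |
| Sessions | 30 (6 weeks × 5 weekdays) |

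**Step 1: try to reproduce the stated total.** Pulses = cycles × bursts × pulses per burst = 20 × 10 × 3 = 600. The stated figure is 1800, and 1800 / 600 = 3.0. It is not reproduced.

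**Step 2: session length for the stated pattern.**
- Counting the gap after the last train: 20 × (2 + 8) = 200 s, or 3 min 20 s.
- Leaving it out: 20 × 2 + 19 × 8 = 192 s, or 3 min 12 s.

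Both are close to the stated 3 min.

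**Step 3: what 1800 pulses would need.** One train holds 10 × 3 = 30 pulses, so 1800 / 30 = 60 trains. These take 60 × 10 = 600 s (10 min), or 60 × 2 + 59 × 8 = 592 s without the last gap.

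**Step 4: what fits in exactly 3 min.** 180 / 10 = 18 trains, and 18 × 30 = 540 pulses.

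**Step 5: readings that might reconcile the figures.**
- *The 8 s runs from the start of one train to the start of the next.* Then 20 trains take 19 × 8 + 2 = 154 s and still give 600 pulses. At most 23 trains start and finish within 180 s (22 × 8 + 2 = 178 s), giving 23 × 30 = 690 pulses. Reaching 1800 would take 59 × 8 + 2 = 474 s.
- *Denser trains.* Getting 1800 from 20 trains needs 1800 / (20 × 3) = 30 bursts per train, or 1800 / (20 × 10) = 9 pulses per burst. The text says 10 and 3.
- *Three 600-pulse runs.* No repeat runs are described. The total is stated per session, and 30 sessions over 6 weeks of weekdays leaves one per day.
- *No gaps at all.* Ten bursts in 2 s is 5 bursts per second, so 180 s would give 180 × 5 × 3 = 2700 pulses. That is not 1800 either.

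None of these gives 1800.

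**Step 6: over the course.** 30 × 600 = 18,000 pulses, against 30 × 1800 = 54,000.

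**The case against.** The strongest reply is that only one number is out of line. The cycle count and the session length agree to rounding (192 to 200 s against 3 min), so a reader would take 1800 as the error. To deliver it, an operator would have to override two stated settings, moving from 20 to 60 trains and from 3 to about 10 minutes. Operators are trained and certified on the device, and all participants are expected to enrol at one institution. If one setting is used throughout, the result belongs to that setting. The seizure argument in section 9.a is also mainly about intensity relative to motor threshold, and the Background and device entries are not themselves wrong.

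Much of this is fair. 1800 is the outlier. The 12 to 20 s over 3 min is rounding, and the 540-pulse figure in Step 4 is no separate error. Divergence between operators is a possibility the text allows, not something shown to happen. Sections 3.a and 5.a rely on the specification; they do not repeat the mistake.

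It does not remove the contradiction. The document never says that 1800 is a slip, and consistent delivery of 1800 pulses cannot be ruled out. The appeal to FDA-approved parameters does not settle the matter, because the protocol gives no other pulse count and its own list of those parameters conflicts with the total that follows. Section 9.a argues partly from intensity, but it also relies on the stimulation parameters as a set.

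Text extraction is not the cause. A break falls just before the session length, but even with the length set aside, 20 × 10 × 3 cannot equal 1800.

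**Conclusion.** The concern holds: the dose is wrong as written and must be corrected. The stated pattern gives 600 pulses per session and the stated total is 1800, a ratio of 3.0. Over 30 sessions that is 18,000 against 54,000 pulses. With the same trains, the session lasts about 200 s in one case and 600 s in the other.

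The pulse comparison is multiplication of the protocol's own figures and needs no outside source. The durations assume the 8 s is a gap between trains; reading it as a start-to-start interval changes the times but not the threefold difference. Which dose is intended cannot be decided from the document. The finding concerns pulse count only, and stimulation intensity is a separate matter.

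**What to change.** 1. The sponsor decides which dose is intended and corrects section 2.a so that cycles, pulses per session and minutes multiply out. With the present trains, the consistent sets are 20 cycles, 600 pulses and about 3 min 20 s, or 60 cycles, 1800 pulses and about 10 min.
2. Use that single specification in the device rationale (section 5.a) and the risk section (section 9.a). If 1800 is intended, the short-session argument in section 3.a needs another look, because a session would last about 10 minutes.
3. Add a CRF field for pulses delivered at each session, and report the dose as delivered.

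The first item removes the contradiction. The other two keep the dependent sections in line and make the dose verifiable afterwards. The cost is a wording amendment, IRB notification and one CRF field, with no added patients or visits.
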